7.1. Study Subjects

7.1.1. Disposition of Subjects

Subject disposition throughout the course of the study will be summarized using a flow chart.

7.1.2. Clinical Investigation Plan (CIP) Deviations

Events within a study that did not occur according to the CIP will be recorded as study deviations in the Case Report Form (CRF). The CIP describes a few potential study deviations:

- The investigator will be responsible for performing the re-evaluation of the subject's chronic medications or HF treatment. Any changes in baseline medications will need to be reported to the ISCC. If no changes were made, rationale as to why changes were not made will need to be provided. Failing to follow these protocol requirements will result in a study deviation.
- Blood work will be performed by the site if PRN intervention is stopped anytime because of safety concern. Blood work will also be performed if 2 rounds PRNs are completed irrespective of whether the intervention is deemed success or failure after 2 PRNs. Investigators will be required to record creatinine, eGFR, K⁺ and Na⁺ in the blood work CRF. Lack of completing this blood work CRF in its entirety will be considered a study deviation.
- Outside of the PRN medication intervention window, subject's blood pressure will be monitored for hypotension per nominal safety threshold of a systolic blood pressure of <85 mmHg or a diastolic blood pressure <40 mm Hg or physician specified threshold, if different. The Investigator will be required to review the 'Exception Report' and determine if clinical actions are necessary. Actions along with rationale will be documented in the CRF. Lack of completing the CRF in its entirety will be considered a study deviation.

Details of the reporting and handling of study deviations can be found in Section 9 of the CIP. Study deviations will be summarized in the study reports based on deviation type, and details of individual study deviations will be listed.

7.1.3. Analysis Sets

For the two primary objectives aiming to characterize the effectiveness and safety of the Integrated Diagnostic Medication Intervention Strategy, a per protocol analysis set will be used. Specifically, all subjects who have received the Integrated Diagnostic Medication Intervention will be included in the analysis for these two objectives.

For the ancillary objective that is to characterize the occurrence of HF events, a per protocol analysis set will be used. Specifically, all the enrolled subjects who have completed the baseline and programming visit will be included.

Per CIP Section 13, all study objectives will be analyzed once the last enrolled subject has completed the 12-month follow-up visit and/or during interim analyses. If data are deemed to sufficiently characterize the study objectives by the sponsor at one of the interim analyses, enrollment and/or follow-up will be stopped. It is planned to conduct the first interim analysis after 100 subjects are enrolled and have completed the baseline and programming visit. If the study continues after the first interim analysis, the second interim analysis will be conducted after 150 subjects are enrolled and have completed the baseline and programming visit.

In addition, there will be a preliminary safety interim data analysis to summarize preliminary safety of PRN intervention. All the subjects who have completed the baseline and programming visit by the time of the analysis will be considered.

7.2. General Methodology

There is no statistical hypothesis for any of the study objectives. Generalized linear models with generalized estimating equation (GEE) will be used to characterize the effectiveness and safety of Integrated Diagnostic Medication Intervention Strategy, and Poisson regression will be used to characterize the occurrence of HF events. These apply to both interim and final analyses. The preliminary safety interim data analysis will be conducted through descriptive statistics.

7.3. Center Pooling

This study could include up to 20 US centers. Data from all the centers will be pooled. For each study objective, center effect will not be considered in the statistical modeling. Instead, for the two primary objectives, the average number of PRN interventions per subject that are effective or safety will be reported for each individual center. Using the effectiveness endpoint as an example, first the percentage of PRNs being effective will be calculated for each subject as the number of effective PRNs divided by the total PRNs that have been implemented for that subject; then the individual percentages will be averaged within each center. Center-specific analysis will not be conducted for the ancillary objective.

7.4. Handling of Missing Data and Dropouts

Because this is a feasibility study and no hypothesis testing is involved in any of the study objectives, the main analysis for each objective will not account for missing data. If missing data becomes a concern, a sensitivity analysis will be considered.

7.5. Adjustments for Multiple Comparisons

There is no statistical hypothesis for any of the study objectives. Therefore, adjustments for multiple comparisons are not applicable.

7.6. Demographic and Other Baseline Characteristics

Subjects' demographic and other baseline characteristics will be summarized using descriptive statistics. For continuous variables, descriptive statistics such as mean, standard deviation, median, the first and third quartiles, and range will be presented. For categorical variables, counts and percentages will be reported.

7.7. Treatment Characteristics

The INTERVENE-HF research system combines integrated device diagnostics based risk stratification algorithm with a guided work flow process handled by a centralized communication center to manage HF patients. Section 7.9.1 and 7.9.2 describe in details the methods that evaluate the effectiveness and safety of this system. Other characteristics of the system will be summarized using descriptive statistics.

7.8. Interim Analyses

In the INTERVENE-HF study, it is planned to have two interim analyses for all study objectives and one preliminary safety interim data analysis.

7.8.1. Interim Analyses

As indicated previously, all study objectives will be analyzed once the last enrolled subject has completed the 12-month follow-up visit and/or during interim analyses. If data are deemed to sufficiently characterize the study objectives by the sponsor at one of the interim analyses, enrollment and/or follow-up will be stopped.

7.8.1.1. Analysis Methods

It is planned to conduct the first interim analysis after 100 subjects are enrolled and have completed the baseline and programming visit. If the study continues after the first interim analysis, the second interim analysis will be conducted after 150 subjects are enrolled and have completed the baseline and programming visit. The same statistical methods will be used for both the interim and final analyses. See section 7.9 for details.

7.8.1.2. Determination of Patients/Data for Analysis

Patients to be analyzed for each study objective at the time of the interim analyses will be determined using the same rules as those described in Section 7.9 for the final analysis. The analysis sets will be per protocol.

7.8.2. Preliminary Safety Interim Data Analysis

This analysis is to summarize preliminary safety of PRN intervention. There is no statistical hypothesis for this analysis. The endpoint includes any adverse event reported per protocol.

7.8.2.1. Analysis Methods

The analysis will occur when 10 PRN interventions have been implemented and the last completed PRN intervention has been followed up for 14 days. Descriptive statistics such as count and percentage will be used. The seriousness and relatedness of adverse events will be based on the Clinical Events Committee (CEC) adjudication. If an adverse event has not been adjudicated by the CEC by the time of the analysis, study investigators' assessment (if available) will be considered. However, the goal of the study team is to have all the adverse events adjudicated for this analysis. The primary interest in the relatedness of adverse events includes but is not limited to safety issues leading to termination of PRN interventions, treatment-related adverse events after implementation of PRN interventions, and HF events occurring during or within 14 days after completion of PRN intervention. Adverse events occurring before and after PRN interventions will be summarized separately.

7.8.2.2. Determination of Patients/Data for Analysis

All the subjects who have completed the baseline and programming visit by the time of the preliminary safety interim data analysis will be included.

7.9. Evaluation of Objectives

7.9.1. Primary Objective #1

To characterize the effectiveness of the Integrated Diagnostic Medication Intervention Strategy in resolving subject risk.

7.9.1.1. Hypothesis

There is no statistical hypothesis for this objective.

7.9.1.2. Performance Criteria and Rationale

Performance criteria and corresponding rationale are not applicable for this objective.

7.9.1.3. Endpoint Definition

Once initiated, the Integrated Diagnostic Medication Intervention Strategy will be regarded as being effective if all the following criteria are met:

- The intrathoracic impedance of a subject recovers per defined criterion after completion of the Integrated Diagnostic Medication Intervention;
- The subject has no HF-related event (as adjudicated by the CEC) during or in the next 14 days after completion of the Integrated Diagnostic Medication Intervention;

NOTE: Intervention for heart failure decompensation (HF event) is defined as an event requiring invasive intervention (i.e. IV diuretics, ultrafiltration, or equivalent) or inpatient hospitalization.

- The subject has not experienced any adverse events that are related to the Integrated Diagnostic Medication Intervention per CEC adjudication and require medical care.

7.9.1.4. Analysis Methods

For each episode that requires intervention as determined by this protocol, the effectiveness of Integrated Diagnostic Medication Intervention Strategy will be evaluated as a binary outcome variable, where 1 = effective and 0 = not effective. During the course of the study, a subject could experience more than one intervention. Therefore, a generalized linear model with the generalized estimating equation (GEE) method will be used to analyze this correlated binary data. The effectiveness rate and its 95% confidence interval (CI) will be calculated based on the log of odds estimated using the GEE.

In the main analysis, there will be no covariates in the generalized linear model, only intercept (β_0) will be estimated. Let π = probability (Integrated Diagnostic Medication Intervention Strategy is effective), then:

$$\beta_0 = \log\left(\frac{\pi}{1 - \pi}\right)$$

To solve for π :

$$\pi = \frac{e^{\beta_0}}{1 + e^{\beta_0}}$$

The analysis will be conducted using PROC GENMOD procedure in SAS similar to the following:

```

proc genmod data=effectiveness descending;
  class pt;
  model effective = /dist=bin link=logit type3;
  repeated subject=pt /type=exch modelse;
  output out=predict predicted=pr_success lower=lower_CI upper=upper_CI;
run;

```

In this procedure, 'effective' is the outcome variable with 1=effective and 0=not effective. 'dist=bin' and 'link=logit' indicates this generalized linear model is based on a logistic regression for binomial distribution. In the 'repeated' statement, 'subject=pt' assumes observations from the same subject are correlated, and 'type=exch' means parameter coefficient(s) in the model will be estimated using GEE. 'predicted=' in the 'output' statement gives the estimated probability of Integrated Diagnostic Medication Intervention Strategy being effective, and its 95% confidence interval based on the parameter estimate of the intercept are from 'lower=' and 'upper='.

If it turns out that the majority of subjects included in the analysis received a single Integrated Diagnostic Medication Intervention, a sensitivity analysis will be conducted through the common logistic regression assuming independent interventions within the same subject. In addition, secondary analysis may be considered to explore the association of covariates such as NYHA class with the effectiveness endpoint.

7.9.1.5. Determination of Patients/Data for Analysis

All subjects who have received the Integrated Diagnostic Medication Intervention will be included. The analysis set is per protocol.

7.9.1.6. Sample Size and Measurement Precision

[figure not shown]
There are no data to help us predict the percentage of OptiVol crossings receiving Integrated Diagnostic Medication Intervention or the effectiveness rate of Integrated Diagnostic Medication Intervention Strategy. Different scenarios have been considered in Table 2 and Figure 2 to estimate the precision on measuring the effectiveness rate of Integrated Diagnostic Medication Intervention Strategy. Figure 2 is a visual illustration of Table 2.

The width of 95% CI for the effectiveness rate represents the measurement precision. Using the first row in Table 2**Error! Reference source not found.** as an example, a total of 70 independent episodes with Integrated Diagnostic Medication Intervention produces a two-sided 95% CI with an actual width of 0.225 when the observed proportion of having effective treatment among those episodes is 0.7. This is based on the exact Clopper-Pearson confidence interval for one proportion assuming independent effectiveness status of Integrated Diagnostic Medication Intervention. Note that each episode is an OptiVol crossing that lead to the initiation of an Integrated Diagnostic Medication Intervention. Note also that for each scenario, we expect a narrower width (i.e. better precision) of 95% CI for the effectiveness rate in the framework of generalized linear model with GEE method. This is because GEE method takes the correlation among the effectiveness status of multiple episodes from the same subject into account, thus presumably results in a smaller standard error of the effectiveness rate.

Table 2: Measurement Precision of Effectiveness Rate for 70-100 Independent Episodes

Sample

Confidence Level	Size (N)	Actual Width (P)	Proportion	Lower Limit	Upper Limit
0.950	70	0.225	0.700	0.579	0.804
0.950	70	0.199	0.800	0.687	0.886
0.950	70	0.154	0.900	0.805	0.959
0.950	80	0.210	0.700	0.587	0.797
0.950	80	0.186	0.800	0.696	0.881
0.950	80	0.143	0.900	0.812	0.956
0.950	90	0.198	0.700	0.594	0.792
0.950	90	0.174	0.800	0.702	0.877
0.950	90	0.135	0.900	0.819	0.953
0.950	100	0.187	0.700	0.600	0.788
0.950	100	0.165	0.800	0.708	0.873
0.950	100	0.127	0.900	0.824	0.951

Figure 2: Illustration of Table 2

7.9.2. Primary Objective #2

To characterize the safety of the Integrated Diagnostic Medication Intervention Strategy in resolving the subject risk.

7.9.2.1. Hypothesis

There is no statistical hypothesis for this objective.

7.9.2.2. Performance Criteria and Rationale

Performance criteria and corresponding rationale are not applicable for this objective

7.9.2.3. Endpoint Definition

Once initiated, the Integrated Diagnostic Medication Intervention Strategy will be regarded as being safe if all the following criteria are met:

- The Integrated Diagnostic Medication Intervention applied to an episode is not terminated due to safety issues;

NOTE: Safety issues include hypotension with/without patient contact and weight loss with patient contact.

- And, the Integrated Diagnostic Medication Intervention applied to an episode has not caused treatment-related adverse events (as adjudicated by the CEC).

7.9.2.4. Analysis Methods

Similar to the effectiveness endpoint of Integrated Diagnostic Medication Intervention Strategy, the safety endpoint of Integrated Diagnostic Medication Intervention Strategy is a correlated binary outcome with 1=safe and 0=not safe. It will be analyzed using a generalized linear model with GEE method. The safety rate and its 95% CI will be calculated based on the log of odds estimated using GEE.

Similar to Section 7.9.1.4, the analysis will be conducted using PROC GENMOD:

```
proc genmod data=safety descending;
  class pt;
  model safe = /dist=bin link=logit type3;
  repeated subject=pt /type=exch modelse;
  output out=predict predicted=pr_success lower=lower_CI upper=upper_CI;
run;
```

where 'safe' is the outcome variable with 1=safe and 0=not safe.

Again, if it turns out that the majority of subjects included in the analysis received a single Integrated Diagnostic Medication Intervention, a sensitivity analysis will be conducted through the common logistic regression assuming independent interventions within the same subject. In addition, secondary analysis may be considered to explore the association of covariates such as NYHA class with the safety endpoint.

7.9.2.5. Determination of Patients/Data for Analysis

All subjects who have received the Integrated Diagnostic Medication Intervention will be included. The analysis set is per protocol.

7.9.2.6. Sample Size and Measurement Precision

The estimated precision of measuring effectiveness rate of Integrated Diagnostic Medication Intervention Strategy under different scenarios illustrated in Table 2 and Figure 2 are applicable to the safety rate as well. Using the first row in Table 2 as an example, a total of 70 independent episodes with Integrated Diagnostic Medication Intervention produces a two-sided 95% CI with an actual width of 0.225 when the observed proportion of having safe treatment among those episodes is 0.7.

7.9.3. Ancillary Objective

To characterize the occurrence of Heart Failure (HF) events in the study subjects.

7.9.3.1. Hypothesis

There is no statistical hypothesis for this objective

7.9.3.2. Endpoint Definition

The endpoint of this objective is the number of HF events per subject, as adjudicated by CEC.

7.9.3.3. Analysis Methods

The number of HF events will be summarized using frequency and percentage, and stratified by the implementation status of Integrated Diagnostic Medication Intervention (1=have ever received the intervention, 0=have never received the intervention). A Poisson regression model will be used to analyze the number of HF events, adjusting for the implementation of Integrated Diagnostic Medication Intervention. The fit of the Poisson regression model will be checked. If over dispersion is a concern, a negative binomial model may be considered.

PROC GENMOD procedure will be used to perform the Poisson regression analysis:

```
proc genmod data=HEvent;
class PRN;
model HEvent = PRN / dist=poisson link=log;
run;
```

where 'HEvent' is the number of HF events per subject, and 'PRN' refers to the implementation status of Integrated Diagnostic Medication Intervention with 1=have ever received the intervention and 0=have never received the intervention.

It is important to note, that those who have received the Integrated Diagnostic Medication Intervention might be sicker when compared to subjects who have never received the Integrated Diagnostic Medication Intervention, and therefore, are more likely to have HF events. Thus, the number of HF events before and after the intervention will be summarized using descriptive statistics for the subjects who have received such intervention.

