1.2 Study Description

The INTERVENE-HF study is a prospective, non-randomized, multi-center (US only), investigational, feasibility study. Patients with heart failure that have an implanted commercially available Medtronic cardiac resynchronization therapy defibrillator (CRT-D) device will be enrolled in the study. The basic INTERVENE-HF research system is comprised of the pre-existing Medtronic, CRT-D device, investigational 2090 programmer software capable of turning ON/OFF the silent OptiVol[®] wireless CareAlert, and the INTERVENE Study Communication Center (ISCC). The ISCC will reside with the Care Management Service (formerly Cardiocom) business unit of Medtronic. The INTERVENE-HF study will have a dedicated team of licensed nurses at ISCC that will guide and monitor subjects through an individualized, physician prescribed medication intervention for diuretics and other acute volume management drugs after their silent OptiVol CareAlert has been transmitted and medication intervention is warranted.

The study is expected to be conducted at up to 20 centers located in the United States. Up to 400 subjects will be enrolled to yield up to 200 eligible subjects that meet screening criteria. This study will be conducted in subjects with an implanted, commercially available, Medtronic, CRT-D device. A detailed list of these devices and model numbers is provided in Table 4. To ensure a widespread distribution of data and minimize center bias in study results, the maximum number of subjects enrolled at a single center is 30 subjects. It is estimated that subject enrollment will take approximately 12 to 18 months. Each enrolled subject will be followed every 2 months from time of enrollment to end of the study. It is anticipated that subjects will participate in the study for a minimum duration of 12 months and up to approximately 30 months. The study will end after the last enrolled subject completes the 12-month follow-up. Because INTERVENE-HF is a feasibility study, it is not intended to show an outcome of improvement. Rather the objective is to test the operational feasibility and safety of device diagnostics *plus* an intervention system as set forth in the primary and secondary objectives. Interim analyses of these objectives will take place and if data are deemed to sufficiently characterize the study objectives by the sponsor at one of these analyses, enrollment and/or follow-up will be stopped.

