7.9 Scheduled follow-up phone calls

Data analyses include follow-up phone calls, regardless of whether the phone call occurs within the window. Therefore, should contact to the subject not be established within the pre-specified window, a late phone call is preferred over a missed phone call.

The participating investigator/study coordinator will attempt to reach the subject for this follow-up phone call for up to ± 14 calendar days from target date listed in Table 13. Follow-up visit windows are based on the day post-OptiVol CareAlert was turned ON.

Note: Because the study is estimated to be completed in approximately 30 months (includes approximately 18 months of enrollment and 12 months of follow-up from the last enrolled subject) window dates are provided for 30 months. If follow up phone calls need to continue beyond 30 months, the windows will continue at 60 day intervals with ± 14 day windows.

Table 13: Data collection and study procedure requirements at subject phone call

Study Follow-up Phone Call	Window (Based on Day OptiVol CareAlert was turned ON)		
	Window Start (days post-OptiVol CareAlert turned ON)	Target (days post-OptiVol CareAlert turned ON)	Window End (days post-OptiVol CareAlert turned ON)
2-Month	46	60	74
4-Month	106	120	134
6-Month	166	180	194
8-Month	226	240	254
10-Month	286	300	314
12-Month	346	360	374
14-Month	406	420	434
16-Month	466	480	494
18-Month	526	540	554
20-Month	586	600	614
22-Month	646	660	674
24-Month	706	720	734
26-Month	766	780	794
28-Month	826	840	854
30-Month	886	900	914

The following information is required to be collected at the follow-up phone call:

- Current Medications or changes in medication
- Document any reportable AEs (refer to section 10 for Adverse Events and Device Deficiencies)
- Record any changes to the CRT-D implanted system
- Worsening HF symptoms
- Recent hospitalizations or surgeries
- Change in co- morbidities

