7.14 Study Exit

At study exit, an eCRF is required for all subjects except in the case of death. Prior to exiting a subject from the study, it is recommended to follow the subject until all ongoing system and/or procedure related AEs are resolved or unresolved with no further actions planned. Following exit, subjects will continue to receive standard medical care with their primary/enrolling physician. Upon exiting from the study, no further study data will be collected and no further study visits will occur for the subject. All data available through the time of the subject's exit will be used for analysis.

Subjects are urged to remain in the study as long as possible but may be exited from the study for any of the following situations:

- Subject has completed follow-up
- Subject lost to follow-up
- Subject death
- Subject has an explant without the intent to re-implant
- Subject did not meet inclusion/exclusion criteria
- Subject did not provide consent or data use protection authorization
- Subject chooses to withdraw (e.g., consent withdrawal, relocation to another geographic location)
- Investigator deems withdrawal necessary (e.g., medically justified, inclusion/exclusion criteria not met, failure of subject to maintain adequate study compliance)
- Lead or generator replacement

If subject is not lost to follow up, the OptiVol alert will be turned off at study exit and the following information is required to be collected:

- Reason for exit (eCRF)
- AE
- Blood work: Includes but not limited to Potassium and Sodium (K⁺ and Na⁺), eGFR, and Hemoglobin.
- OptiVol Information Report from 2090 Programmer: Print AFTER using the software to disable the OptiVol alert. See User Manual for instructions on how to access the software and how to turn off the OptiVol alert.

Note that an in-person visit will be required to turn OFF the OptiVol alert in the CRT-D device by use of a Medtronic 2090 programmer. See User Manual for instructions on how to access the software and how to turn off the OptiVol alert.

In the case that the subject is determined to be lost to follow-up, details of a minimum of two attempts and the method of attempt (e.g., one letter and one phone record or two letters) to contact the subject must be recorded. In addition, follow the regulations set forth by the governing IRB.

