10.2 Adverse Event and Device Deficiency Assessment

10.2.1 Adverse Events

All system related events, all cardiovascular-related events, all events that may be associated with the PRN intervention and all SAEs will be collected throughout the study duration, starting at the time of signing the consent form.

An exception to this subset of collected events mentioned above, would be the protocol-initiated PRN intervention, which will not be collected on the Adverse Event form (AE CRF).

When the protocol initiated PRN intervention occurs, it will be collected on the ISCC Notification form.

Reporting of these events to Medtronic will occur on an Adverse Event (AE) Form, including a description of AE, date of onset of AE, date of awareness of site, treatment, resolution, assessment of both the seriousness and the relatedness to the investigational device. Each AE must be recorded on a separate AE Form. Subject deaths are also required to be reported. Refer to section 10.5 for Subject Death collection and reporting requirements.

Documented pre-existing conditions are not considered AEs unless the nature or severity of the condition has worsened. Adverse events impacting users or other persons are also reportable during the course of the study.

For AEs that require immediate reporting, initial reporting may be done by phone, secure file transfer system, or on the eCRF completing as much information as possible. The AE eCRF must be completed as soon as possible. Refer to the study contact list provided in the center's study documents binder/investigator site file or refer to the contact information provided on the title page.

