- (1) 55% of the enrolled subjects who meet screening criteria and complete the baseline and programming visit will have at least one OptiVol crossing within the 12 months of follow-up; and
- (2) The distribution for those experiencing OptiVol crossings during the 12 months of follow up is the same as the results from the unpublished data.

As shown in Table 18, this leads to approximately 233 OptiVol crossings in 110 subjects (55% of 200 subjects) to be observed in the INTERVENE-HF study. Furthermore, literature

has indicated that 45% of OptiVol crossings are HF related²⁰. This means about 105 out of the 233 OptiVol crossings would require PRN implementation in this study.

Table 18: Number of OptiVol crossings expected from 110 (55% of 200) subjects

Assumption		Estimation	
Crossing(s)	% of subjects having the crossing(s)	Expected # of subjects having the crossings	Expected # of crossings
1	39%	43	43*1=43
2	28%	31	31*2=62
3	19%	21	21*3=63
4	9%	10	10*4=40
>4	5%	5	5*5=25
Total		110	233

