13.5.3 Analysis Methods

The number of HF events will be summarized using frequency and percentage, and stratified by the implementation status of Integrated Diagnostic Medication Intervention (1=have ever received the intervention, 0=have never received the intervention). A Poisson regression model will be used to analyze the number of HF events, adjusting for the implementation of

Integrated Diagnostic Medication Intervention. The fit of the Poisson regression model will be checked. If over dispersion is a concern, a negative binomial model may be considered. It is important to note, that those who have received the Integrated Diagnostic Medication Intervention might be sicker when compared to subjects who have never received the Integrated Diagnostic Medication Intervention, and therefore, are more likely to have HF events. Thus, the number of HF events before and after the intervention will be summarized using descriptive statistics for the subjects who have received such intervention.

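### The Poisson model for HF events has no follow-up-time offset, although planned follow-up runs from 12 to about 30 months

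*SAP*

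**What the plan says.** Protocol 13.5.3 states that "A Poisson regression model will be used to analyze the number of HF events", adjusted for whether the intervention was implemented. SAP 7.9.3.3 gives the code: "model HEvent = PRN / dist=poisson link=log". The outcome is the number of CEC-adjudicated HF events per subject (SAP 7.9.3.2), and PRN is a cumulative ever/never indicator. Model fit is to be checked, with a negative binomial model as a possible fallback for overdispersion. Neither document mentions an offset, person-time or a follow-up covariate for this objective.

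Follow-up is unequal by design. Protocol 1.2 says "subjects will participate in the study for a minimum duration of 12 months and up to approximately 30 months", because everyone is followed until the last subject reaches 12 months, and "It is estimated that subject enrollment will take approximately 12 to 18 months". Protocol 7.14 adds: "All data available through the time of the subject's exit will be used for analysis". SAP 7.8.1.1 applies the same methods at interims triggered when 100 and 150 subjects have completed the baseline and programming visit.

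Both documents warn that PRN recipients may be sicker. For that reason they add a descriptive summary of HF event numbers before and after the intervention in those recipients. They do not say when the before period starts. Adverse events "will be collected throughout the study duration, starting at the time of signing the consent form" (Protocol 10.2.1), while for the scheduled calls "Follow-up visit windows are based on the day post-OptiVol CareAlert was turned ON" (Protocol 7.9).

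**The concern.** A Poisson model of counts without an offset compares mean counts, not rates. That is harmless when everyone is observed for the same time, or when group membership is unrelated to follow-up. Neither holds here. Being an ever-PRN subject is something one accumulates, so a subject watched for 30 months is more likely to be classed as ever-PRN than one watched for 12, and also has more time in which to have HF events. The fitted ratio then mixes event rate with length of observation. A negative binomial fallback changes the variance, not this.

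The before/after summary has a parallel problem, since the two periods differ in length and the counts have no denominator.

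The objective is to characterize HF event occurrence, and the study is meant to inform a pivotal trial. An event rate carried into that planning should be a rate.

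**Working it through.** **Plan's own figures.** Protocol Table 18: 43×1 + 31×2 + 21×3 + 10×4 + 5×5 = 233 crossings per 200 subjects in 12 months. At 45% HF-related, 233 × 0.45 = 104.9, the plan's 105. Both reproduce. Per subject-year this is 233/200 = 1.165 crossings and 1.165 × 0.45 = 0.524 PRN interventions.

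**Chance of ever having a PRN.** The plan assumes that "55% of the enrolled subjects who meet screening criteria and complete the baseline and programming visit will have at least one OptiVol crossing" within 12 months. A uniform crossing rate would imply 1 − exp(−1.165) = 69%, so the rate must vary between subjects. With gamma variation, shape k solves 1 − (1 + 1.165/k)^(−k) = 0.55, giving k = 1.12. Then, for follow-up T in years,

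P(ever PRN | T) = 1 − (1 + 0.524T/k)^(−k),

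which is about 35% at 12 months and 58% at 30 months.

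**Expected ratio.** If everyone has the same HF rate r, independent of PRN, the expected count in a group is r × mean T in that group. The rate cancels:

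ratio = mean T in ever-PRN / mean T in never-PRN.

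If T were equal for all, this would be exactly 1.

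**Final analysis.** Even accrual (assumed) makes T uniform from 12 to 24 months (12-month accrual) or 12 to 30 months (18-month accrual). Exit rates are assumed, because the documents give none; exits are taken as independent of PRN propensity.

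| Scenario | 12-month accrual | 18-month accrual |
|---|---|---|
| Mean T, ever vs never, no exits (months) | 18.4 vs 17.7 | 21.7 vs 20.3 |
| Ratio, no exits | 1.04 | 1.07 |
| Ratio, 5% exits per year | 1.08 | 1.11 |
| Ratio, 10% exits per year | 1.12 | 1.16 |

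**Interims.** With 100 or 150 of 200 subjects in, entry has been spread over 6 or 9 months (12-month accrual) or 9 or 13.5 months (18-month accrual). No data cutoff is stated, so three are shown.

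| Cutoff after the triggering subject's baseline visit | Ratio |
|---|---|
| Same day | 1.36 to 1.39 |
| 3 months later | 1.09 to 1.18 |
| 6 months later | 1.04 to 1.10 |

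**Size against noise.** HF rates of 0.3 and 0.6 per year are assumed.

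- Final analysis, no exits: the bias is 0.2 to 0.5 of a standard error, and the 95% CI spans a factor of 1.3 to 1.5 each way. In 20,000 simulated trials per setting, the median ratio was 1.04 or 1.07 without the offset and 1.00 with it. The ratio exceeded 1 in 58% to 68% of trials (about 50% with the offset). The CI excluded 1 in 5.4% to 8.3% without the offset, against 4.5% to 5.1% with it.
- Final analysis, 10% yearly exits: the bias is 0.5 to 1.0 standard error, and the ratio exceeded 1 in 69% to 83% of trials.
- Same-day interim cutoff: about 1 to 14 HF events are expected in the ever-PRN group, so the CI spans a factor of about 1.9 to 7.5 each way and the bias is 0.3 to 1.1 standard errors.

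**Before/after in PRN recipients**, no change in HF rate, no exits, final analysis. From CareAlert ON to first PRN, and from first PRN to study end, the mean periods are 7.4 and 11.0 months (12-month accrual) or 8.5 and 13.2 months (18-month). The after/before count ratio is 1.48 or 1.56. If the before period starts at consent, assumed 30 days earlier, it is 1.31 or 1.40.

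**The case against.** The strongest reply concerns weight. The objective is ancillary, has no hypothesis and feeds no stated decision rule. The SAP introduction says further analyses are expected, so rates per subject-year could be reported without an amendment. The ever/never ratio already carries a severity warning, and an offset would not remove that confounding. All of this stands and limits the importance of the point. It does not make the specified code right: the warning is about sicker patients, not time at risk, and permission to do more is not a plan to do it.

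The larger numbers are also conditional. The interim figures near 1.4 need a same-day cutoff and come with very few events. The exit figures assume that exits are unrelated to PRN propensity. If the exit hazard averages 0.10 per year and is proportional to that propensity, the final ratios fall to 1.07 and 1.10 (12- and 18-month accrual). The size shrinks but the direction stays.

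Finally, the protocol records HF events in the 6 months before enrollment (Table 12; section 7.8). Adding 6 months to the before period gives 11.0/13.4 = 0.82 and 13.2/14.5 = 0.91, which reverses the direction. That history falls outside the CEC-adjudicated endpoint, so it is not the natural reading. It does show that the before/after result depends on a window the SAP never defines.

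**Conclusion.** The concern holds. As coded, the ratio confounds HF rate with length of follow-up, and its expectation is above 1 at equal HF rates whenever follow-up varies, though not in every single trial. The size to quote is 1.04 to 1.07 at the final analysis without early exits. The exit and interim figures should be quoted only with their assumptions. All sizes rest on even accrual, a PRN rate constant over time within a subject, gamma variation between subjects fitted to the plan's 55%, and HF events independent of PRN. The before/after counts are not interpretable without a defined window and a denominator. This should be fixed, but it is a correction to a descriptive ancillary estimate and leaves both primary objectives untouched.

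**What to change.** In Protocol 13.5.3 and SAP 7.9.3.3:

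- Derive follow-up time from OptiVol CareAlert ON to exit or data cutoff (minimum 1 day). Add its log as an offset in the Poisson model and in any negative binomial fallback, and count HF events over the same interval.
- State the data cutoff for each interim.
- Report HF events per subject-year by group beside the frequency table.
- Report before/after as rates per unit of follow-up, with the before period starting at CareAlert ON.
- Keep the severity caveat. The offset does not remove severity confounding, nor the problem of classifying a subject's whole follow-up by a PRN received later. Splitting person-time at the first PRN is an optional addition that addresses the latter.

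The cost is one derived variable, one model option and a few lines of text. The dates are already collected: CareAlert ON and OFF in the disposition logs (Protocol 17.1), PRN initiation on the ISCC Notification form (10.2.1), and exit and death on their own forms (7.14, 10.5.1). The change should be in place before the first interim.
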